6.4 PROCEDURE

Refer to the Instructions For Use (IFU) for procedural steps.

Fractional Flow Reserve (FFR) is an index determining the functional severity of narrowing(s) in the coronary arteries. FFR specifically identifies which coronary narrowing(s) are responsible for significantly obstructing the flow of blood to the heart muscle. FFR is used in conjunction with cardiac catheterization by placing the pressure wire distal to the coronary lesion and measuring pressure inside the artery. The pressure wire is then retracted until pressure is measured in the entire coronary artery.

The following data points will be collected during the procedure for all evaluated lesions (index or secondary procedures):

- Measurements of Pd/Pa
- Measurements of FFR with Adenosine induced hyperemia (IC or IV)
- MACE assessment (required)
- Prospective treatment decisions; initial treatment plan documentation shall be prior to FFR.

Other indices may be collected, according to the investigator's clinical practice and availability of appropriate devices (index or secondary procedures), as follows;

- IMR measurements
- CFR measurements
- Measurements of FFR with Contrast induced hyperemia
- Measurements of any additional novel resting indices (RI)

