12.1.2 Analysis Populations

Data from up to 2000 subjects enrolled in this study will be collected and reported. The statistical analyses described in this section will be performed for all enrolled subjects, ACS subjects and stable coronary artery disease subjects separately.

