12.1.3 Statistical Method and Analysis

This section describes the statistical method and analysis per subject basis unless otherwise specified. If more than one lesion is measured for a subject, the data analysis may be performed and presented on a per lesion basis, as appropriate.

The following criteria will be used to define the variables per subject level for subject with multiple lesions:

- Treatment decision is defined as “changed” if there is at least one decision change based on FFR for multiple lesions; if none of the decisions has been changed for the multiple lesions, the treatment decision is defined as “unchanged”.
- For all the continuous variables of FFR, resting indices, CFR, contrast FFR, and RRR, we will use the lowest value in all lesions as the value for that variable in each subject. For the continuous variable of IMR, we will use the highest value in all lesions as the value for IMR in each subject.

The following cutoff values will be used to categorize a continuous variable into a binary variable:

- FFR group is defined as “low FFR” if it is equal to or below 0.8 (the cutoff value of 0.8 is selected in line with contemporary guidelines and previous findings¹¹). However, since this is an observational study, there are no mandated cutoff values for this. Therefore, we will also use cutoff value of 0.75¹² in the analysis.
- Resting indices group is defined as “low resting indices” if it is equal to or below 0.86 (the cutoff value of 0.86 is selected based on previous findings that a baseline Pd/Pa \leq 0.86 is associated with a positive predictive value of 100% for FFR measurement¹³). We will also use the cutoff value of 0.92¹⁴ in the analysis.

Clinical Investigational Plan

- CFR is defined as “low CRF” if it is below 2.0 (the cutoff value of 2.0 is selected based on previous findings^{15,16}).
- IMR is defined as “high IMR” if it is equal to or above 25 (the cutoff value of 25 is selected based on previous findings¹⁷).
- Contrast FFR is defined as “low Contrast FFR” if it is equal to or below 0.83 (the cutoff value of 0.83 is selected based on previous findings¹⁸).
- RRR is defined as “low RRR” if it is smaller than 2.0 (the cutoff value of 2.0 is selected based on previous findings¹⁹).

The following statistical analysis will be performed for each of the study objectives:

1. Characterize the frequency of change in treatment plan when FFR is used compared to the initial decision based on angiography alone

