Frequency and percentage of change in treatment decisions when FFR is used compared to the initial decision based on angiography alone will be presented both per subject level and per lesion level.

2. Characterize the 12-month clinical outcomes (MACE) in subjects in whom the use of FFR did not lead to a change in treatment decision vs. subjects in whom the use of FFR led to a change in treatment decision.

12-month MACE event rate will be summarized using frequency and percentage. Fisher Exact test will be performed to evaluate the association between 12-month MACE event and prospective treatment decisions, i.e. change or no change, based on FFR measurements. A repeated measures logistic regression with generalized estimating equations (GEE) per lesion level will be performed if needed.

3. Characterize the 12 month clinical outcomes (MACE) by FFR values and resting indices respectively.

Fisher Exact test will be performed to evaluate the association between 12-month MACE event and binary FFR and binary resting indices variables respectively using the following FFR and resting indices groups:

- 1) Low FFR group ($FFR \leq 0.8$) and high FFR group ($FFR > 0.8$).
- 2) Low FFR group ($FFR < 0.75$) and high FFR group ($FFR \geq 0.75$).
- 3) Low resting indices group ($Pd/Pa \leq 0.86$) and high resting indices group ($Pd/Pa > 0.86$).
- 4) Low resting indices group ($Pd/Pa \leq 0.92$) and high resting indices group ($Pd/Pa > 0.92$).

A repeated measures logistic regression with generalized estimating equations (GEE) per lesion level will be performed if needed.

A logistic regression will be performed to evaluate the association between 12-month MACE event and continuous FFR and continuous resting indices respectively. A repeated measures logistic regression with generalized estimating equations (GEE) per lesion will be performed if needed.

4. Compare resting indices with FFR values.

Kappa coefficient will be used for binary variables, and correlation will be used for continuous variables to examine agreement between FFR values and resting indices.

5. Characterize the 12 month clinical outcomes (MACE) by other PressureWire-derived indices (CFR, IMR, contrast FFR, RRR).

Clinical Investigational Plan

Fisher Exact test will be used for binary variables, and logistic regression will be used for continuous variables to evaluate the association between 12-month MACE event and other PressureWire-derived indices (CFR, IMR, contrast FFR, RRR) respectively.

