6. Compare other PressureWire-derived indices (CFR, IMR, contrast FFR, RRR) with FFR values

Kappa coefficient will be used for binary variables, and correlation test will be used for continuous variables to examine agreement between FFR values and other PressureWire-derived indices (CFR, IMR, contrast FFR, RRR) respectively.

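### Objective 6 computes kappa and correlation for CFR, IMR and contrast FFR only in lesions where they happened to be measured, with no check on, or allowance for, selection by lesion severity

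*Combined protocol and SAP*

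**What the plan says.** Section 6.4 of the combined protocol and SAP sets two tiers of collection. Pd/Pa and adenosine FFR belong to the first: "The following data points will be collected during the procedure for all evaluated lesions". IMR, CFR, contrast FFR and novel resting indices belong to the second: "Other indices may be collected, according to the investigator's clinical practice and availability of appropriate devices". RRR, which objectives 5 and 6 also analyse, is not named in either list.

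The only ordering rule in the text of 6.4 concerns the treatment plan: "initial treatment plan documentation shall be prior to FFR". No order relative to FFR is given for the optional indices.

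For objective 6, section 12.1.3 states: "Kappa coefficient will be used for binary variables, and correlation test will be used for continuous variables to examine agreement between FFR values" and the other indices. For objective 5 it states: "Fisher Exact test will be used for binary variables, and logistic regression will be used for continuous variables to evaluate the association" with 12-month MACE. Section 12.1.2 says the analyses are "performed for all enrolled subjects, ACS subjects and stable coronary artery disease subjects separately". It defines no set of subjects or lesions with an optional index. Neither objective has a missing-data rule, a comparison of measured with unmeasured lesions, or any weighting.

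The default unit is the subject. For subjects with several lesions, "we will use the lowest value in all lesions as the value for that variable in each subject" (the highest for IMR). Section 12.1.3 permits a per-lesion analysis but does not commit objective 6 to one.

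**The concern.** Kappa and correlation depend on the spread of severity among the lesions analysed. Lesions near the FFR cutoff are hard to classify consistently, and lesions far from it are easy. If operators add an optional index mainly in borderline lesions, agreement with FFR will look worse than in all evaluated lesions. If they mainly skip borderline lesions, it will look better.

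Objective 6 would then mix the performance of the index with the habits of the operators. Differences between indices, or between ACS and stable subjects, could reflect who was measured. The planned output would not let a reader tell these apart.

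The per-subject rule adds a second problem. Suppose lesion A has low FFR and no contrast FFR, and lesion B has high FFR and high contrast FFR. The rule pairs A's FFR with B's contrast FFR and scores a disagreement, although the only lesion with both values agrees.

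**Working it through.** The documents give no expected kappa, correlation or measured fraction for objective 6, so there is no stated figure to reproduce. The check asks how far kappa can move.

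**Inputs from section 12.1.3:** low FFR is ≤ 0.80; low contrast FFR is ≤ 0.83.

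**Assumed inputs:** FFR is normal with mean 0.82 and SD 0.10. Contrast FFR = FFR + 0.03 + error with SD 0.04, so r = 0.10/√(0.10² + 0.04²) = 0.93. The grey zone is FFR 0.75 to 0.85. An index is measured in a fraction a of grey-zone lesions and b of the others.

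**Step 1, grey-zone share.** Φ(0.3) − Φ(−0.7) = 0.618 − 0.242 = 0.376; the others make up 0.624.

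**Step 2, agreement within each band** (simulated, 4 million lesions):
- Grey zone: both low 0.339, FFR low only 0.136, contrast FFR low only 0.147, both high 0.379. Observed agreement is 0.718; low FFR 0.475; low contrast FFR 0.486.
- Others: 0.378, 0.009, 0.012, 0.602. Observed agreement is 0.980; low FFR 0.387; low contrast FFR 0.390.

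**Step 3, mix the bands as measured.**
- g = 0.376a/(0.376a + 0.624b)
- Po = 0.718g + 0.980(1 − g)
- F = 0.475g + 0.387(1 − g) and C = 0.486g + 0.390(1 − g)
- Pe = FC + (1 − F)(1 − C)
- κ = (Po − Pe)/(1 − Pe)

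For a = 60%, b = 10%: g = 0.2256/0.2880 = 0.783. Po = 0.562 + 0.213 = 0.775. F = 0.456 and C = 0.465, so Pe = 0.212 + 0.291 = 0.503. κ = 0.272/0.497 = 0.55.

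| Measured (grey zone / others) | g | Po | Pe | κ | r |
|---|---|---|---|---|---|
| all, or a random fraction | 0.376 | 0.881 | 0.512 | 0.76 | 0.93 |
| 60% / 20% | 0.644 | 0.811 | 0.505 | 0.62 | 0.89 |
| 60% / 10% | 0.783 | 0.775 | 0.503 | 0.55 | 0.85 |
| 60% / 5% | 0.879 | 0.750 | 0.502 | 0.50 | 0.79 |
| 10% / 60% | 0.091 | 0.956 | 0.521 | 0.91 | 0.95 |

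**Step 4, sensitivity and specificity at FFR 0.80.** With all lesions they are 0.865 and 0.893. Under 60% / 10% they fall to 0.347/(0.347 + 0.108) = 0.76 and 0.428/(0.428 + 0.117) = 0.785.

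If selection depends only on FFR status (40% of high-FFR and 5% of low-FFR lesions measured), they stay at 0.865 and 0.893, because both condition on FFR status. Kappa still falls. The low-FFR share becomes 0.05 × 0.42/(0.05 × 0.42 + 0.40 × 0.58) = 0.083. Po = 0.083 × 0.865 + 0.917 × 0.893 = 0.891. C = 0.083 × 0.865 + 0.917 × 0.107 = 0.170, so Pe = 0.083 × 0.170 + 0.917 × 0.830 = 0.775. κ is about 0.51.

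**Step 5, weighting.** Weighting measured lesions by 1/a and 1/b returns g to 0.376 and κ to 0.76, provided a and b are both above zero. If b = 0, only the grey-zone value remains, (0.718 − 0.501)/(1 − 0.501) = 0.43, and weighting cannot repair it.

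**Step 6, selection on Pd/Pa.** With an assumed Pd/Pa–FFR correlation of 0.7, unweighted κ was about 0.71. Weighting on FFR band alone gave 0.71 to 0.75, depending on the set-up. Weighting on Pd/Pa gave 0.76. The weights therefore need both variables.

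**Step 7, other inputs.** With FFR mean 0.83, SD 0.09 and contrast-FFR correlation 0.90, κ goes from 0.71 to 0.50 under 60% / 10% and to 0.87 under 10% / 60%. For CFR with assumed r of 0.50, the corresponding values are 0.32, 0.18 and 0.43. For IMR uncorrelated with FFR there is no bias.

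**The case against.** The strongest reply is that optional measurement is the design of an observational study of routine practice, that no success criterion hangs on objective 6, and that the two drivers named in 6.4 are investigator practice and device availability, neither of which is the FFR value. If availability decides, independently of the lesion, the measured lesions are in effect a random sample and kappa stays at 0.76. All selection rates above are assumptions. This stands, and it limits the point to a possible bias.

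A reader might infer four stronger things that the documents do not support:
- *That operators add an index after seeing FFR.* The visible text states no order. The flow chart in section 6.1 is not shown and the case report forms are under separate cover, so either may fix or record the order. The point does not need it, since selection on Pd/Pa also moves kappa.
- *That every agreement measure is biased.* Step 4 shows that sensitivity and specificity do not move when selection depends only on FFR being above or below 0.80.
- *That this is partial-verification bias.* That term applies when the reference is missing. Here the reference, FFR, is planned for every evaluated lesion and the index is missing.
- *That the MACE association in objective 5 is biased.* Selection on a predictor need not bias a regression on that predictor, and no bias was shown. What follows is only that the results apply to the measured subset.

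It is also fair to say that lesion-level weights do not fit the per-subject rule. The fix must therefore change the unit as well.

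**Conclusion.** The point holds for objective 6 as a cheap improvement. The plan analyses an optionally measured subset as if it were unselected. If measurement depends on FFR or Pd/Pa, the planned kappa and correlation are subject to selection bias in either direction. Under the assumed contrast-FFR model, kappa of 0.76 becomes about 0.50 to 0.62 with grey-zone selection and about 0.91 with the reverse.

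These sizes rest on assumed distributions, correlations and measured fractions; the documents supply only the cutoffs. They establish that the bias is possible, not that it occurs. Under measurement unrelated to the lesion it is nil. For objective 5 the conclusion is limited to whom the results describe.

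**What to change.** In section 12.1.3, objective 6:

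- (a) Tabulate FFR and Pd/Pa in lesions with and without each optional index, overall and for ACS and stable subjects.
- (b) Compute agreement on index and FFR values paired within the same lesion, with standard errors clustered by subject, in place of per-subject extremes that may come from different lesions.
- (c) Beside the unweighted values, report values weighted by the inverse of the measured fraction within FFR band, Pd/Pa band and presentation (ACS or stable).
- (d) Where a band has no measured lesion, limit the conclusion to the bands that have some.

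For objective 5, show table (a) and state that the results apply to the measured subset. If the case report form does not already do so, record whether each optional index was taken before or after FFR was known.

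The cost is small. FFR and Pd/Pa are planned for every evaluated lesion, so (a) to (d) need no new measurement, and the order of measurement is at most one added field per index. Weighting usually loses some precision. In one simulated setting (2000 lesions, about 602 measured, the step 7 contrast-FFR model) it did not: the SD of kappa was 0.031 weighted and 0.036 unweighted. Weighting corrects only for selection on recorded variables.

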6.5 SCHEDULED FOLLOW-UPS

Follow-up visits will occur at Discharge and 1-year.

The following assessments will be completed at the Discharge visit:

- MACE assessment

The following assessment will be completed at the 1-Year visit (±30 days):

- MACE assessment

Note: the 1-Year visit may be conducted via a phone call to the subject.

6.6 INTERIM VISITS

An Interim Visit is defined as any visit that occurs as a result of a potential MACE event outside the windows of the standard assessment schedule.

The following assessments will be completed at an Interim visit:

- MACE assessment

6.7 SUBJECT STUDY COMPLETION

When the subject's participation in the clinical study has been completed after one year follow up, no further patient data will be collected.

Clinical Investigational Plan

6.8 CRITERIA AND PROCEDURES FOR SUBJECT WITHDRAWAL OR DISCONTINUATION

Subjects must be informed about their right to withdraw from the study at any time and for any reason without sanction, penalty or loss of benefits to which the subject is otherwise entitled and withdrawal from the study will not jeopardize their future medical care or relationship with the investigator. Subjects will be asked to specify the reason for the termination, but have the right not to answer.

The investigator may decide to withdraw a subject from the study at any time with reasonable rationale. The subject's future care will not be influenced by a decision, voluntary or otherwise, to withdraw from the study. All reasonable efforts should be made to retain the subject in the clinical study until completion of the study.

Reasons for subject's withdrawal include, but are not limited to:

- Subject refuses to continue participating in the study
- Subject does not meet the inclusion/exclusion criteria
- Subject is deceased (cause must be documented)
- Subject's participation is terminated by the PI or investigator, although the subject consented, since participation is no longer medically appropriate
- Subject is 'lost to follow-up': Subject does not adhere to the scheduled follow up visits but has not explicitly requested to be withdrawn from the clinical study. (This does not apply to missed visits). Site personnel should at all times make all reasonable efforts to locate and communicate with the subject in order to achieve subject compliance to the scheduled follow up visits:
 1. A subject will be considered 'Lost to Follow Up' after a minimum of 2 phone calls of a physician or delegate at the investigational site to the subject or contact. These 2 phone calls need to be documented in the subject's hospital records.
 2. If these attempts are unsuccessful, a letter should be sent to the subject's last known address or general practitioner (GP) and a copy of this letter should be maintained in the subject's hospital records.

If a subject withdraws from the clinical study, the site will record the subject's reasons for withdrawal, on a Withdrawal CRF.

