4.3 RISKS ASSOCIATED WITH PARTICIPATION IN THE CLINICAL STUDY

The risks of taking part in the PRESSUREwire study and undergoing FFR assessment or alternative indices are the same whether the subject receives the assessment as part of the study or outside of the study.

Clinical Investigational Plan

Refer to the Instructions for Use (IFU) in the package labeling for potential risks associated with an SJM PressureWire™.

A risk of study participation is that confidentiality cannot be guaranteed. Investigational site personnel, SJM, and SJM representatives will take measures to de-identify study subject personal health information in an effort to maintain subject anonymity.

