8.1.4 Serious Adverse Device Effect (SADE)

Adverse device effect that has resulted in any of the consequences characteristic of a serious adverse event or that might have led to any of these consequences if suitable action had not been taken or intervention had not been made or if circumstances had been less opportune.

8.2 PROCEDURE FOR ASSESSING, RECORDING, AND REPORTING ADVERSE EVENTS, DEVICE DEFICIENCIES/COMPLAINTS, ADVERSE DEVICE EFFECTS, SERIOUS ADVERSE EVENTS, AND SERIOUS ADVERSE DEVICE EFFECTS:

Safety surveillance within this study and the safety reporting both performed by the investigator, starts as soon as the subject is enrolled in this study. The safety surveillance and the safety reporting will continue until the last investigational visit has been performed, the subject is deceased, the subject/investigator concludes his participation into the study or the subject/investigator withdraws the subject from the study, except as otherwise specified in the CIP.

Events considered reportable to sponsor are:

- Major adverse cardiac events (MACE) defined as all cause death, documented non-fatal myocardial infarction, and unplanned hospitalization leading to urgent revascularization
 - Myocardial infarction is defined according to the Universal Classification of Myocardial Infarction¹¹ (Appendix B)
 - Unplanned hospitalization leading to urgent revascularization is defined as unexpected hospitalization due to persisting or increasing complaints of chest pain (with or without ST-T changes) AND a revascularization is performed within the same hospitalization.
- Adverse device effects

All above events will be reported to the Sponsor, as soon as possible, but no later than 72 hours of first learning of the event. These will be reported to the Sponsor on dedicated case report forms or through the EDC system. The Investigator will record all adverse events and device deficiencies on the appropriate case report forms

Additional information may be requested, when required, by the Sponsor in order to support the reporting of AEs to regulatory authorities.

The Sponsor will ensure that all events and device deficiencies are reported to the relevant authorities as per regulations.

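### Investigator withdrawal ends event reporting with no duty to seek later outcomes, so 12-month MACE can be understated if withdrawal is related to worsening health

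*Combined protocol and SAP*

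**What the plan says.** Section 6.8 gives the investigator two routes to withdraw a subject who has not asked to leave. One is general: "The investigator may decide to withdraw a subject from the study at any time with reasonable rationale". The other is a listed reason, that the subject's "participation is terminated by the PI or investigator, although the subject consented, since participation is no longer medically appropriate". Neither comes with criteria. The same section asks sites to make reasonable efforts to keep subjects in the study. The only item it requires at withdrawal is the reason, on a Withdrawal CRF.

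Section 8.2 sets when surveillance and reporting stop. Among the stopping points is that "the subject/investigator withdraws the subject from the study, except as otherwise specified in the CIP". The same section gives the endpoint: "Major adverse cardiac events (MACE) defined as all cause death, documented non-fatal myocardial infarction, and unplanned hospitalization leading to urgent revascularization".

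Section 8.3.1 requires all subject deaths to be put on a Death CRF and reported within 72 hours of the site learning of them. Section 3.4 requires withdrawn subjects to be accounted for under an identification code.

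Section 12.1.3 says of the analysis that "12-month MACE event rate will be summarized using frequency and percentage", followed by Fisher exact tests and logistic or GEE models. Sections 12.1.2 and 12.1.3 contain no denominator, censoring or missing-data rule for subjects without 12-month status.

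**The concern.** The study observes a measurement made in routine care. Section 4.3 says the risks "are the same whether the subject receives the assessment as part of the study or outside of the study". The only scheduled contact after discharge is at one year, and section 6.5 adds: "Note: the 1-Year visit may be conducted via a phone call to the subject". Ending a subject's active participation therefore need not end the collection of outcomes. As written, however, investigator withdrawal ends both.

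A judgement that participation is no longer medically appropriate may well be related to declining health, and so to the risk of death or another MACE component. Loss of that kind is outcome-related. Events after withdrawal that are not collected cannot be restored at the analysis stage; a sensitivity analysis can only bound them. MACE at 12 months is the outcome in objectives 2, 3 and 5.

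**Working it through.** The plan states no MACE rate, withdrawal rate or power, so there is no figure of its own to reproduce. The check has two parts.

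**1. Is there a duty to collect outcomes after investigator withdrawal?**

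- Section 8.2 ends reporting at withdrawal, subject to exceptions stated elsewhere in the plan.
- Section 8.3.1 can be read as such an exception for deaths. It depends on the site becoming aware, creates no duty to look, and does not cover infarction or urgent revascularization.
- The retention effort in section 6.8 applies before withdrawal. The accounting in section 3.4 concerns identification, not outcomes.
- Other leavers are better covered. For loss to follow-up, section 6.8 requires two documented calls and then a letter to the last address or the general practitioner. Section 16.1 keeps enrolled subjects in follow-up if the study is terminated early or suspended. Nothing comparable applies to one subject withdrawn by the investigator.

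So no such duty exists beyond reporting deaths that come to the site's notice.

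**2. How large could the effect be?**

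Input from section 12.1.1: N = 2000 (approximate). Assumed inputs: b, the 12-month MACE risk in retained subjects; w, the share withdrawn by the investigator; d, the event risk of those subjects after withdrawal. For simplicity, none of them had a MACE before withdrawal and none of their later events is captured.

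- True rate = b(1 − w) + wd
- Reported rate = b(1 − w) if withdrawn subjects stay in the denominator as event-free, or b if they are left out
- Relative understatement = 1 − reported/true

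| b | w | d | Events in retained | Events lost | True rate | Reported (event-free / left out) | Understatement (event-free / left out) |
|---|---|---|---|---|---|---|---|
| 5% | 0.5% | 10% | 1990 × 5% = 99.5 | 10 × 10% = 1 | 100.5/2000 = 5.025% | 4.975% / 5.000% | 1.0% / 0.5% |
| 5% | 1% | 30% | 1980 × 5% = 99 | 20 × 30% = 6 | 105/2000 = 5.25% | 4.95% / 5.00% | 5.7% / 4.8% |
| 5% | 2% | 50% | 1960 × 5% = 98 | 40 × 50% = 20 | 118/2000 = 5.90% | 4.90% / 5.00% | 16.9% / 15.3% |
| 10% | 1% | 30% | 1980 × 10% = 198 | 20 × 30% = 6 | 204/2000 = 10.2% | 9.9% / 10.0% | 2.9% / 2.0% |
| 10% | 2% | 50% | 1960 × 10% = 196 | 40 × 50% = 20 | 216/2000 = 10.8% | 9.8% / 10.0% | 9.3% / 7.4% |

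If withdrawn subjects are left out and d equals b, there is no bias. In the target of 500 ACS subjects, w = 2% and d = 30% would lose 500 × 2% × 30% = 3 events.

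**The case against.** The strongest reply is that the plan already protects deaths. Section 8.2 allows exceptions, and section 8.3.1 requires all subject deaths to be reported without excluding withdrawn subjects. This stands in part. A reader might infer that deaths after withdrawal are never collected, and the documents do not support that: a death the site hears of is reportable. What remains is that nobody has to find out, and that the two non-fatal components are not covered.

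A second reply is that the clause will seldom be used, because an observational study with one remaining contact gives little medical reason to withdraw anyone, and section 6.8 asks for retention and a rationale. This also has force. A reader might infer that the clause will be applied mainly to the gravely ill. That is a plausible inference from its wording, but no section says so or says how often it will be used.

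Third, a reader might expect biased comparisons in objectives 2, 3 and 5, or a larger loss in ACS subjects. Nothing in the documents shows that this withdrawal would differ by treatment change, index value or presentation.

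Fourth, section 6.8 lists death itself as a withdrawal reason, from which a reader might infer that deaths are dropped from MACE. They are not: death is a MACE component with its own CRF, and section 8.2 names it separately from withdrawal. The listing is disposition bookkeeping.

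Finally, section 12 has no rule for any subject without 12-month status, and this clause is only one part of that wider gap. That is correct, but an analysis rule cannot supply outcomes whose collection has stopped.

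**Conclusion.** The point holds in limited form. Following sections 6.8 and 8.2 as written stops active outcome collection in subjects withdrawn by the investigator, and 12-month MACE can be understated if those withdrawals are related to worsening health.

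The size cannot be derived from the documents. The central illustration, a relative understatement of about 5-6%, and the range of roughly 0.5-17% rest on an assumed 5% MACE risk in retained subjects and on the assumed withdrawal shares and later risks tabulated. They are not bounds, and they fall if the underlying MACE risk is higher. Expressing the loss as a share of deaths alone would give a larger percentage, but the endpoint is the composite. No direction of bias between groups can be stated. This is a modest weakness, worth correcting because the remedy is cheap.

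**What to change.** State in sections 6.8 and 8.2 that investigator withdrawal of an eligible subject ends active participation but not outcome collection. MACE and vital status are still obtained to 12 months from hospital records, the general practitioner or a contact person, where consent and local law allow. Collection ends only if the subject withdraws consent. The investigator's discretion to withdraw a subject can remain; restricting withdrawal to revoked consent would go further than the problem requires.

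The cost is protocol wording, a records or practitioner check for a few subjects, and possibly a line in the consent template. Whether that line is needed cannot be judged here, because the template is held under separate cover. No visit or procedure is added.

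### Section 6.8 lets a subject be coded lost after calls and a letter without any check of vital status or the site's own records, so 12-month MACE and death may be understated

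*Combined protocol and SAP*

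**What the plan says.** Section 6.5 sets the schedule: "Follow-up visits will occur at Discharge and 1-year". It adds that "the 1-Year visit may be conducted via a phone call to the subject". The 1-year contact is thus the only scheduled one after discharge. Section 6.6 provides interim visits, but only when a potential MACE prompts one.

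Section 6.8 makes loss to follow-up a withdrawal reason. A subject may be considered lost "after a minimum of 2 phone calls of a physician or delegate at the investigational site to the subject or contact". If the calls fail, a letter should go to the subject's address or to the GP. Both steps sit under a general duty: "Site personnel should at all times make all reasonable efforts to locate and communicate with the subject". The stated purpose of that duty is compliance with the scheduled visits. A known death is a separate withdrawal reason, with its cause documented.

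Section 8.2 makes all-cause death a MACE component, alongside non-fatal MI and unplanned hospitalization with urgent revascularization. Section 8.3.1 requires deaths to be reported within 72 hours, counted from when the site learns of them. Section 12.1.3 summarizes 12-month MACE as a frequency and percentage and relates it to treatment change and to the indices by Fisher tests and logistic regression. Section 12 has no rule for subjects without a 12-month outcome.

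**The concern.** A subject who has died does not answer the telephone. If the contact person cannot be reached either, and the letter brings no reply, the site has met the requirements of 6.8 and may record the subject as lost. Section 6.8 mentions hospital records only as the place to file the calls and the letter. Staff may therefore have open the record that shows a death, MI admission or revascularization without being asked to look for one.

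The other routes to an event are passive. Interim visits need the subject to come to the site's notice, and death reporting starts from awareness. The remote monitoring in section 10 reviews source documents for reported events, so it will not find one that nobody reported.

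At stake are the 12-month MACE rate, its death component, and objectives 2, 3 and 5, which all use MACE. If loss depends on outcome, analysis of the observed data cannot restore the missing events. Censoring or excluding lost subjects assumes that loss is unrelated to outcome, which is the assumption in doubt.

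**Working it through.** The plan gives no loss, MACE or death rate, and section 12.1.1 states that no formal sample-size calculation was done. There is no figure to reproduce. What follows is a sensitivity calculation.

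**Inputs.** From section 12.1.1: N = 2000, with a target of 500 ACS subjects. Assumed: MACE in retained subjects p = 5%; loss L = 5% or 10%; MACE in lost subjects q = 3%, 5%, 10% or 20%.

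**Formulas.**
- True rate = (1 − L)p + Lq.
- Lost subjects excluded: reported rate = p, so error = p − true = L(p − q).
- Lost subjects counted as event-free: reported rate = (1 − L)p, so error = −Lq.
- Events missed = N × L × q.

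**Example.** L = 5%, q = 10%: true rate = 0.95 × 5% + 0.05 × 10% = 4.75% + 0.50% = 5.25%. Events missed = 2000 × 0.05 × 0.10 = 10.

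| L | q | True rate | Error if excluded (reported 5.00%) | Error if counted event-free (reported 4.75% or 4.50%) | Events missed |
|---|---|---|---|---|---|
| 5% | 3% | 4.90% | +0.10 | −0.15 | 3 |
| 5% | 5% | 5.00% | 0 | −0.25 | 5 |
| 5% | 10% | 5.25% | −0.25 | −0.50 | 10 |
| 5% | 20% | 5.75% | −0.75 | −1.00 | 20 |
| 10% | 3% | 4.80% | +0.20 | −0.30 | 6 |
| 10% | 5% | 5.00% | 0 | −0.50 | 10 |
| 10% | 10% | 5.50% | −0.50 | −1.00 | 20 |
| 10% | 20% | 6.50% | −1.50 | −2.00 | 40 |

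Errors are in percentage points.

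**Direction.** With exclusion the sign follows p − q: understated if the lost have more events, unbiased if they have the same, overstated if they have fewer. Counted as event-free, the rate is understated whenever any lost subject had an event.

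**Against sampling error.** The 95% half-width is 1.96 × √[r(1 − r)/N], with r the true rate. For N = 2000 it is about 0.98 points at 5.25%, 1.00 at 5.50% and 1.08 at 6.50%. At L = 5%, q = 10%, the error is a quarter to a half of that. At L = 10%, q = 20%, it exceeds it on either convention. For 500 subjects the half-width is about 1.95 points at 5.25% and 2.16 at 6.50%, so under the same assumed rates the error stays inside sampling error there.

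**Deaths (assumed).** With 2% in retained subjects, 8% in lost subjects and 5% loss: 0.95 × 2% + 0.05 × 8% = 1.9% + 0.4% = 2.3%, against a reported 2.0% (excluded) or 1.9% (event-free).

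**The case against.** Section 6.8 is more than two unanswered calls. Two is a minimum, the calls may go to a contact person, a letter to the address or GP follows, and there is a general tracing duty. A contact or GP could well disclose a death. Events that reach the site during the year are caught through interim visits and 72-hour reporting. The consent template, case report forms and Data Management Plan are separate documents and may hold contact or vital-status fields. This is also an observational study with no formal power calculation.

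Much of this stands. A reader might infer that 6.8 stops at two calls, or that there is no contact at all between discharge and 1 year; the text supports neither. The remaining gap is narrower. The calls item can be read as allowing lost status before the letter. The letter may go to the address instead of the GP, no reply is needed, and nobody is told to ask whether the subject is alive.

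A reader might also want to delete the parenthesis "This does not apply to missed visits", since only one post-discharge visit can be missed. The wording is unclear, but it can be read as saying that a missed visit alone is not loss. Deleting it could make subjects easier to code as lost. Discharge is also listed as a follow-up visit. The deletion is not recommended.

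**Conclusion.** The gap is real and worth closing: 6.8 permits loss to be coded without a check of vital status or of the site's own records, in a study whose main clinical outcome includes all-cause death. The consequence is a risk of understatement.

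A reader might infer that MACE is certainly biased downward. The documents do not support that, because they fix neither the denominator nor the handling of a missing 12-month outcome, and they say nothing about the risk of lost subjects. Nor do they support a definite direction for the associations in objectives 2, 3 and 5, which depend on how loss is spread across the groups compared.

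On the assumed rates, with lost subjects excluded, a reported 5.0% corresponds to a true rate of about 4.8–6.5%. The upper end, 30% above the reported figure (6.5/5.0 = 1.30), needs 10% loss and a fourfold event rate among the lost at the same time. At 5% loss and double the event rate, the true rate is 5.25%.

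**What to change.** Amend section 6.8 along these lines:

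> Before a subject is coded lost to follow-up, and where consent and local law allow, the site must: (a) complete the calls and the letter; (b) check its own hospital records for death, MI or revascularization; (c) ask the contact or GP explicitly about vital status; (d) consult a public death register where one is accessible; and (e) record the date the subject was last known alive and the source of that information.

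The separate consent template should cover this check, and the Withdrawal form should hold the date and source. Leave the missed-visit parenthesis in place. Stating the MACE denominator in section 12 would complement this change but cannot replace it, because an analysis rule does not recover events that were never collected.

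The cost is protocol, consent and form wording plus minor site effort for each unreachable subject, with no added visit. Register access and privacy rules differ by country, so completeness will vary across the roughly 200 centers; recording the source makes that variation visible.
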